### 5.2 Exclusion Criteria

(1) The following conditions exist at the fracture site: infection, osteofascial compartment syndrome, osteitis, pathological fracture, open fracture, severe tissue or vascular and nerve injury, or insufficient bone mass of the affected limb affecting screw implantation, etc.

(2) Abnormal liver and kidney function with clinical significance (ALT,

AST 2 times the upper limit of normal value and Cr 2 times the upper limit of normal value);

(3) Abnormal coagulation function with clinical significance (APTT > 2

times the upper limit of normal value);

(4) Patients with difficult-to-control diabetes (any blood glucose > 11.1mmol/L or glycosylated hemoglobin > 9%);

(5) Past allergies to silk protein materials;

(6) Mental illness;

(7) Patients who cannot guarantee to quit smoking during the fracture healing period;

(8) Pregnant or lactating women or women of childbearing age who plan to get pregnant within 6 months;

(9) Those who have participated in other pre-clinical trials within 1 month before the trial;

(10) Those who are considered inappropriate to participate in the clinical trial.

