# 7.2 Description of Security Parameters

7.2.1 Vital Signs: Body temperature, respiration, heart rate, blood pressure;

Recording Time: Screening period, before surgery, during surgery, within 1 week after surgery ( $\leq 7$  days), 6 weeks after surgery  $\pm 1$  week, 12 weeks after surgery  $\pm 1$  week, 24 weeks after surgery  $\pm 4$  weeks, 48 weeks after surgery  $\pm 4$  weeks after surgery, 72 weeks after surgery  $\pm 4$ weeks.

7.2.2 Laboratory Examination: Coagulation function, blood routine, urine routine, blood biochemistry;

Recording Time: Screening period, within 1 week after surgery ( $\leq 7$ 

days), 24 weeks after surgery  $\pm$  4 weeks, 48 weeks after surgery  $\pm$  4 weeks after surgery, 72 weeks after surgery  $\pm$  4 weeks.

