# **Trial Procedure**

#### 2.1 Screening Period (V0 period: -7-0 days)

Informed consent must be signed prior to any trial-related procedure, after which subjects are assigned a unique screening number that remains unchanged throughout the trial. If the subject is undergoing elective surgery, it is at the discretion of the investigator whether to re-examine the subject if the preoperative examination exceeds the acceptable time range.

(1) Sign informed consent;

(2) Demographic data: gender, age, height, weight;

(3) Complete medical history: previous disease history within 3 months before signing the informed consent, drug use history, smoking history, drinking history, surgical history and allergy history within 1 month;

(4) Vital signs: body temperature, respiration, heart rate, blood pressure;

(5) Blood pregnancy test: only applicable to women of childbearing age;

(6) Bone mineral density examination (test site);

(7) Blood glucose test: including blood glucose and glycated hemoglobin, only for diabetic patients;

(8) Coagulation function test: prothrombin time (PT), activated partial thromboplastin (APTT), fibrinogen (FIB), thrombin time (TT);

(9) Blood routine: hemoglobin (HB), red blood cell count (RBC), white blood cell count (WBC), platelet count (PLT), hematocrit (Hct);

(10) Urine routine: urinary white blood cells (WBC), urinary protein(PRO), urinary red blood cells (RBC), urinary glucose (GLU);

(11) Blood biochemistry: creatinine (Cr), Urea nitrogen (BUN) / Urea, alanine aminotransferase (ALT), aspartate aminotransferase (AST);

(12) C-reactive protein;

(13) Infectious disease examination: HBSAg, HBsAb, HBeAg, HBeAb,

HBcAb, HCV-rna/ HCV-antibody, syphilis TPPA, HIV antibody;

- (14) X-ray examination;
- (15) Determine the inclusion and exclusion criteria;
- (16) VAS score;
- (17) Recording device defects;
- (18) Record drug combination.

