B. Unqualified Criteria: If the clinical healing rate of fracture is different between the test product and the control product 24 weeks after surgery (experimental group-control group)95%CI lower limit $\leq -10\%$, the clinical validation can be considered to have failed.

6. Criteria and Reasons for Terminating the Trial on Statistics

Not applicable

7. Statistical Methods for All Data, Along With Treatment of Missing, Unused, or Erroneous Data (Including Dropouts and Withdrawals) and Unreasonable Data.

A. Characteristics of the cases

Enrollment and completion: The number of enrolled and completed cases was summarized, and the list of dropped cases was listed.

General information and baseline characteristics: Demographic information and other disease history of the subjects were statistically described.

According to the numerical characteristics of the variables, T-test/corrected T-test was used to compare the age, blood pressure and other quantitative data of the two groups of subjects. Chi-square test/exact probability method was used to compare the qualitative variables such as gender and past medical history of the subjects between the groups. The Wilcoxon rank sum test was used to compare the ordered

classified data between groups.

Baseline: Baseline is defined as the basic situation of the subject before clinical operation.

B. Analysis of effectiveness evaluation indicators

Analysis of main evaluation indicators: The main evaluation index was the clinical healing rate of fracture at 24 weeks after surgery, and the difference of 95% confidence interval between the experimental group and the control group was calculated.

Analysis of secondary evaluation indicators: clinical healing rate of fractures and performance indicators of pain scoring instruments at 12, 48 and 72 weeks after surgery were statistically described by descriptive methods of qualitative or quantitative data according to the characteristics of variable types, and comparison between groups was performed by Chi-square test/exact probability /t test.

C. Analysis of security indicators

The occurrence of adverse events was clinically observed, event name, start time, end time, severity, corrective treatment, and relationship with the experimental product were recorded, and the incidence of adverse events was calculated and compared between groups. Study discontinuation due to adverse events and the occurrence of serious adverse events should be specifically noted.

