For various safety indicators such as vital signs and laboratory tests,

T-test/corrected T-test /Wilcoxon rank sum test were used for comparison between groups according to the numerical characteristics of variables; Chi-square test/exact probability method was used for comparison between groups for qualitative data; Wilcoxon rank sum test or CMH chi square test was used for ordered classified data.

8. Procedures for Deviation from the Original Statistical Plan

The implementation shall be strictly in accordance with the requirements stipulated in 7. If other statistical methods not specified in the program are needed, an application shall be submitted to the Ethics committee for approval before implementation.

9. Selection Criteria and Reasons for Subjects Included in the Analysis

Full Analysis Set (FAS) is a set of subjects that are as close as possible to the ideal in line with the principles of intentionality. The data set is derived from the elimination of subjects from all enrolled subjects by a minimum and reasonable method.

Per Protocol Set (PPS), Also known as a valid case, valid sample, or evaluable case sample. It is a dataset generated from a subset of cases that are fully compliant with the trial protocol and is a subset of the total analysis set. Adherence includes considerations such as the treatment received, the feasibility of the main measure, and the absence of significant violations of the protocol.

Safety Analysis Set (SS): When performing a safety evaluation, the set of subjects used for aggregation is called a safety analysis set. The safety data set shall include all subjects who have used this tester.

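### The SAP tests numeric laboratory values between groups but plans no count of subjects whose results become abnormal after surgery, and no link to their screening values

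*SAP*

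**What the plan says.** Vital signs and laboratory tests share one sentence in SAP section 7C. For numeric variables, "T-test/corrected T-test /Wilcoxon rank sum test were used for comparison between groups according to the numerical characteristics of variables". The sentence goes on: "Chi-square test/exact probability method was used for comparison between groups for qualitative data", and "Wilcoxon rank sum test or CMH chi square test was used for ordered classified data". It names no visit, no change from screening, no abnormal category or grade, and no count of affected subjects.

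Other parts of the plan bear on this:

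- **Baseline.** SAP section 7A states "Baseline is defined as the basic situation of the subject before clinical operation". Section 7C does not use it.
- **Collection.** For laboratory tests, Protocol 7.2.2 gives "Recording Time: Screening period, within 1 week after surgery", then 24, 48 and 72 weeks. Each subject therefore has a pre-operative value. No laboratory tests are listed at 6 or 12 weeks (Trial Procedure 2.4 and 2.5).
- **Cut-off.** The only multiples of an upper limit for ALT, AST and Cr are in the exclusion criteria (Protocol 5.2, item 2): "AST 2 times the upper limit of normal value and Cr 2 times the upper limit of normal value", with ALT named just before.
- **Description.** SAP section 2, like the protocol's Statistical Analysis section 2, calls for the mean, standard deviation, median, minimum and maximum of numeric variables, and counts and percentages of categorical ones.
- **Adverse events.** SAP section 7C compares their incidence between groups.

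**The concern.** A test of group values asks whether two distributions are shifted. A safety reviewer also asks how many subjects developed a clearly abnormal result, in which arm, and whether it was there before surgery. A few large rises can leave the group mean inside the normal range and hardly change the ranks.

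This matters here because laboratory tests are a named safety parameter (Protocol 7.1), the protocol says no screw of the same principle and material exists in China (Experimental Design, section 2), and follow-up was set at 18 months so that safety could be fully observed (Protocol 5.7).

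Timing matters too. SAP section 8 holds the analysts strictly to section 7 and sends any unlisted statistical method to the ethics committee. Cut-offs chosen after the data are seen would also be post hoc.

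**Working it through.** **1. The plan's own figures.** The documents give no figure for the laboratory analysis, so only the group size can be reproduced. From the SAP section 3A formula: (1.96 + 0.8416)² × (2 × 0.955 × 0.045) / 0.10² = 7.849 × 0.08595 / 0.01 = 67.5, so 68 per group. With 15% dropout, 68 / 0.85 = 80 per group, 160 in total. Both match the SAP, and sample size is not at issue.

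**2. What each planned output would show about a few large rises.**

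| Output | Shows | Does not show |
|---|---|---|
| t or Wilcoxon test | shift in mean or ranks | which or how many subjects |
| Maximum | that one extreme value exists | how many, whether new, whether it lasts |
| Chi-square, exact, CMH | counts, if a category exists | anything for numeric tests, as no category is defined |
| Adverse-event incidence | rises reported as events | rises not reported, as no rule says when to report |

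**3. Assumptions for a size (none is in the documents).** ALT log-normal, median 20, upper limit 40, log-SD 0.3 to 0.6; 80 per arm; 4 test-arm subjects near 120 (3 times the limit), none in control.

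**4. Expected signal, t test.** Mean = 20 × exp(s²/2); SD = mean × √(exp(s²) − 1).

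- s = 0.3: control mean 20.9, SD 6.4. Test mean = 0.95 × 20.9 + 0.05 × 120 = 25.9, still under 40. Test SD = √(0.95 × 6.4² + 0.05 × 0.95 × 99.1²) = 22.5. SE = √((22.5² + 6.4²)/80) = 2.6. Ratio = 5.0/2.6 = 1.9.
- s = 0.6: control mean 23.9, SD 15.8; test mean 28.7, SD 26.0; SE 3.4. Ratio = 4.8/3.4 = 1.4.

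Both ratios fall short of 1.96.

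**5. Expected signal, Wilcoxon.** P(test > control) = 0.95 × 0.5 + 0.05 × 1 = 0.525. Null SE = √(161/(12 × 80 × 80)) = 0.0458, so z = 0.025/0.0458 = 0.55. Power is about P(Z > 1.41) + P(Z < −2.51) = 0.079 + 0.006 = 8.5%.

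**6. Simulation under the same assumptions.** With 4 raised subjects, Welch is significant in about 22-39% of trials (highest at log-SD 0.3) and Wilcoxon in about 7-8%. With 3, the figures are 14-17% and 6-7%. With 5 and log-SD 0.3, Welch reaches 67%.

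**7. A second set of assumptions.** Median 22, CV 40%, limit 40, rises of 3 to 6 times the limit, 68 per arm, none raised in control:

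| Raised in test arm | Welch | Wilcoxon | Fisher p for the count |
|---|---|---|---|
| 2 | 4% | 5% | 0.50 |
| 3 | 15% | 7% | 0.24 |
| 4 | 40% | 8% | 0.12 |
| 5 | 69% | 11% | 0.058 |
| 6 | 91% | 12% | 0.028 |

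Testing change from screening instead (correlation 0.6) gives 13% and 6% at 3 subjects, and 40% and 8% at 4: practically no gain.

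**8. The count as a display.** With 4 of 80 against 0 of 80, the difference is 5.0%, Newcombe 95% CI −0.5% to 12.2%, Fisher p = 0.12. If the true rate in an arm were 3%, the chance that at least one such subject appears is 1 − 0.97⁸⁰ = 91% (87% with 68).

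**The case against.** Four objections carry weight.

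- **The sentence is broader than its numeric clause.** It provides for qualitative and ordered safety data. That stands as far as the methods go, but without a defined category they have nothing to act on for ALT, AST or Cr.
- **Extremes are not hidden.** In the example above, the tabulated maximum would show a value near 120, and a large rise could be reported as an adverse event. Both are true. Neither gives the number of subjects or a comparison with screening, and event reporting depends on investigators who are not blinded.
- **A count is no better as a test.** This stands in full. Fisher's exact test needs 6 against 0 of 68, where Welch already reaches 91% under the second set of assumptions.
- **The scenario is assumed.** This also stands. The documents do not say that harm from this implant would take the form of a few large rises, and the 2-times multiple is an entry criterion, not a safety threshold.

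A reader might infer that the trial would declare laboratory safety on a non-significant p-value. The documents do not support that: the only pass/fail rule, in SAP section 5, concerns the healing rate. A reader might also infer that the tests are insensitive because the screening value is left out. Step 7 shows otherwise. The screening value matters for deciding whether an abnormality is new.

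**Conclusion.** The point holds as a gap in the planned display. No output in either document counts subjects with new abnormal laboratory values or relates them to their screening value, although the data for this are collected. The planned tests are a poor substitute when 2 to 4 subjects are affected. Under the first set of assumptions, with 4 of 80, Welch detects about 22-39% and Wilcoxon about 7-8%. Welch improves at 5 to 6 subjects if the spread is low; Wilcoxon stays at 12% or below in step 7.

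These percentages rest on an assumed ALT distribution and size of rise. The absence of a category does not. It would go too far to say that large rises would go unseen, since the maximum and the adverse-event analysis give partial cover. The primary analysis is unaffected. The size was worked out for laboratory values only, and the documents offer no limit for vital signs, so the change below is confined to laboratory tests.

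**What to change.** In SAP section 7C, add by arm:

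1. A shift table (below, within or above the normal range) from screening to each scheduled post-operative laboratory visit (within 1 week, 24, 48 and 72 weeks) and to the worst post-operative value.
2. The number and percentage of subjects newly above 2 times the upper limit for ALT, AST and Cr, with the between-arm difference and its 95% CI. The multiple is the one in Protocol 5.2 and serves here as a reporting cut-off only. Judge newness against each subject's own screening value.
3. A listing of those subjects.

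Keep the group summaries as description.

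Before tabulating coagulation, reconcile Protocol 7.2.2, which includes it after surgery, with Trial Procedure 2.3 and 2.6 to 2.8, which do not list it.

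The cost is a few standard tables from values already scheduled, and intervals that will be wide at this sample size. The tables also need each laboratory's reference range in the database; the documents do not say whether the case report form records it.

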#### 4.2 Before Surgery

(1) Only those patients who meet the indication criteria should be selected.

(2) The condition described in the contraindications section above should be avoided.

(3) In the process of transportation and storage, avoid collision, scratches

or other forms of damage to the implant. Special care should be taken to make the storage environment of the implant.

(4) The surgeon should be familiar with the use of this product and its supporting instruments before use, and confirm that they are ready before the operation.

(5) The type of implant that should be used in each surgical patient and the approximate size range should be determined before the operation begins. A sufficient number of implants of various sizes should be prepared for surgery, including those larger and smaller than expected.

(6) Unless packaged in sterile form, all instruments should be cleaned and sterilized prior to use.

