#### 4.3 During Surgery

(1) For Easy and Safe Screw Insertion:

A. The fracture site should be anatomic reduction or functional reduction. The 1.2mm Kirchner needle should be drilled to the required depth, and the nail path should be established along the Kirchner needle using a hollow drill.

B. Insert the appropriate size tap along the Kirschner needle to form the thread path. The size is consistent with the intended screw length. Screw in to the same depth as the corresponding screw length. Screw into the appropriate depth, counterclockwise out of the tap.

C. Select the appropriate size of the bio-type bone hollow screw and

press the screw head into the tail of the screw to ensure that the whole screw can be picked up. Screw along the Kirschner needle until complete implantation into the bone. The screw and screw are kept parallel to the direction of the bone.

(2) Ensure aseptic operation during the surgery.

(3) Peripheral nerves and blood vessels should be protected during operation.

(4) Breakage, slip or misuse of an instrument or implant during implantation may result in injury to the patient or the surgery.

(5) For more detailed surgical instructions, please refer to the appropriate surgical technical literature.

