#### 5.3 Remove Criteria

(1) No devices were used after enrollment.

(2) Violation of inclusion or exclusion criteria.

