#### 5.6 Group Entry Time

After signing the informed consent form, meeting the inclusion criteria and not meeting the exclusion criteria, the time when the subject underwent randomization was the enrollment time.

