#### 2.2 Day of Surgery (Stage V1: Day 0)

- (1) Vital signs: body temperature, respiration, heart rate, blood pressure;
- (2) Random grouping;
- (3) Record surgical information;
- (4) Instrument performance index;
- (5) Recording device defects;
- (6) Record adverse events;
- (7) Records of combined drug use (except glucose, normal saline and

narcotic drugs);

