# Requirements for Reporting Adverse Events and Device Defects

#### (1) Definition and Reporting of Adverse Events

#### A. Definition of adverse events

Adverse events refer to adverse medical events that occur during clinical trials of medical devices, whether or not they are related to the experimental medical devices. Adverse events were recorded from device use.

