#### (2) Device Defect

Device defect refers to the unreasonable risks that may endanger human health and life safety under normal use of medical devices in the course of clinical trials, such as label errors, quality problems, failures, etc. In the course of this clinical trial, if the use of devices fails due to device defects, the investigator shall conduct routine treatment according to clinical needs. The investigator should document all discovered device defects that occur during clinical trials.

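### Protocol 5.3(1) removes randomised subjects in whom no device was used, with no exception when a defect in the assigned screw is the reason

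*SAP*

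**What the plan says.** **Removal rule.** Protocol 5.3 gives two removal criteria. The first is "No devices were used after enrollment". No reason for non-use is distinguished.

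**Timing.** Under Protocol 5.6, "the time when the subject underwent randomization was the enrollment time". The day-of-surgery visit (Trial Procedure 2.2) lists "Random grouping" among its steps. Protocol section 2 (Masking) says that the researchers cannot be blinded because the products look different.

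**Device failure is foreseen.** The Device Defect section says that "if the use of devices fails due to device defects, the investigator shall conduct routine treatment according to clinical needs" and that discovered defects are to be documented. Protocol 4.3 warns that "Breakage, slip or misuse of an instrument or implant during implantation may result in injury to the patient or the surgery". Protocol 4.2 asks that "A sufficient number of implants of various sizes should be prepared for surgery".

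**Analysis sets.** SAP 9 describes the FAS as all enrolled subjects less a minimal, reasonable elimination. It does not mention 5.3. For safety, "The safety data set shall include all subjects who have used this tester". I read the last words as the screw of either arm. Neither document defines *used* for an attempt that fails.

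**Reporting.** Device defects are recorded at every visit from V0 to V7. Protocol 7.1 does not list them as a safety parameter, and SAP 7C names no comparison of them. SAP 7A provides a list of dropped cases but no count of defects by arm.

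**The concern.** A defect that stops the surgeon from using the allocated screw is a consequence of the allocation. It is unlike the second criterion in 5.3, which concerns eligibility. Because 5.3(1) operates after randomisation and the surgeon knows the arm, removal for non-use can differ between arms for reasons linked to the product. The randomised comparison no longer protects against that.

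Two things are at stake. If 5.3 is applied to the FAS, the primary comparison omits subjects for whom the device could not be used. Whatever is done with the FAS, a difference between arms in defect-related abandonment would appear in no table that the plan names, although the data are collected. The test screw is made of silk fibroin, and the protocol states that no screw of the same principle and material exists in China, so this is information a reader would want.

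**Working it through.** **1. Who is affected.** Reading 5.3(1) with Protocol 4.2, 4.3 and the Device Defect section gives three cases.

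| Case | Device used? | Consequence |
|---|---|---|
| Defect found before use, no study screw implanted | No | Removed by 5.3(1); outside the safety set |
| Defective screw replaced by another of the assigned type | Yes | 5.3(1) does not apply |
| Screw breaks or slips on insertion, routine treatment follows | Arguably yes | Probably kept, but *used* is undefined |

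Only the first case is clearly removed. Protocol 4.2 makes the second likely to be more common than the first.

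**2. The plan's own sample size.** Inputs from SAP 3: healing 95.5% in both arms, margin -10 points, two-sided alpha 0.05, power 80%.

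n = (1.960 + 0.842)² × 2 × 0.955 × 0.045 / 0.10² = 67.5, so 68 per group. With 15% dropout, 68 / 0.85 = 80 per group, 160 in all. Both figures reproduce.

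**3. Effect on the primary result, only if 5.3 cuts the FAS.** The documents give no defect rate, so these counts are assumptions: 80 randomised per arm; control 76/80 healed; 3 test subjects with no screw because of a defect, none in control; 4 of the other 77 test subjects not healed. The SAP does not name an interval method, so two are shown.

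Wald lower limit: d − 1.96 √[p₁(1−p₁)/n₁ + p₂(1−p₂)/n₂], where d = p₁ − p₂.

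Newcombe lower limit: d − √[(p₁ − l₁)² + (u₂ − p₂)²], where l₁ and u₂ are Wilson limits.

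| Handling of the 3 subjects | Test arm | Newcombe (points) | Wald (points) |
|---|---|---|---|
| Removed | 73/77 | -8.2 | -7.1 |
| Kept, 0 not healed | 76/80 | -7.8 | -6.8 |
| Kept, 1 not healed | 75/80 | -9.4 | -8.4 |
| Kept, 2 not healed | 74/80 | -11.0 | -9.99 |
| Kept, 3 not healed | 73/80 | -12.5 | -11.6 |

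Against the -10 criterion in SAP 5, the conclusion changes only with at least 2 of 3 not healed (Newcombe) or all 3 (Wald). If all 3 heal, removal is slightly unfavourable to the test screw.

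These subjects receive routine treatment. With non-healing probability q, P(at least 2 of 3) = 3q²(1−q) + q³:

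- q = 4.5%: 0.0058 + 0.0001 = 0.6%
- q = 10%: 0.027 + 0.001 = 2.8%
- q = 20%: 0.096 + 0.008 = 10.4%

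P(all 3) = q³ = 0.01%, 0.1% and 0.8%.

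**4. What a by-arm defect table would show.** Assumed counts out of 80 randomised per arm, Newcombe 95% interval:

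| Test v control | Difference (points) | 95% CI | Fisher p |
|---|---|---|---|
| 1 v 0 | 1.3 | -3.4 to 6.7 | 1.00 |
| 3 v 0 | 3.8 | -1.5 to 10.5 | 0.25 |
| 5 v 0 | 6.3 | 0.5 to 13.8 | 0.059 |
| 6 v 0 | 7.5 | 1.4 to 15.4 | 0.028 |

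If these are all subjects of the first kind in step 1, the safety set contains none of them in either arm. At 5 v 0 the interval and the exact test disagree about 0.05, so that count should not be read as a threshold.

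**The case against.** **The safety set is conventional.** A set based on exposure is normal practice, and someone who never received a study screw has no implant exposure. Adding subjects whose package was merely opened would dilute the adverse-event denominator. This stands: the set should stay, with a failed attempt defined as use.

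**Adverse events.** Since "Adverse events were recorded from device use", a reader might infer that harm around a failed attempt would go unrecorded. The documents do not support that. Protocol 7.2.3 starts recording before surgery, and Trial Procedure 2.2 lists adverse events on the day of surgery.

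**Partial coverage elsewhere.** The device performance index covers packaging, labelling, supporting equipment and ease of implantation. Trial Procedure 2.2 schedules it on the day of surgery, and SAP 7B appears, in garbled wording, to compare it between groups. The safety indicators in SAP 7C are introduced by an open-ended phrase, with chi-square or exact tests for qualitative data. Some defects could therefore surface by arm. Still, none of the index's four items records a defective or abandoned screw, and defects are not named in 7C.

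**Rarity and missing detail.** Spare implants should make abandonment uncommon, every count above is assumed, and an undefined word or unnamed table would on its own be only missing detail. This lowers the weight of the point. It does not remove it, because 5.3(1) is a stated rule that excludes randomised subjects without regard to cause.

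**Conclusion.** The point holds in a limited form. Protocol 5.3(1) is a post-randomisation removal that depends on an unblinded surgeon's decision and makes no exception for the defect-related failure that the protocol itself foresees. It clearly reaches only subjects who end with no study screw.

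A reader might infer that the primary analysis excludes these subjects, or that the non-inferiority result could readily be reversed. Neither is supported. SAP 9 does not tie 5.3 to the FAS, and its wording neither requires nor prevents the exclusion. Even with three test-arm cases, none in control and removal from the FAS all assumed, crossing -10 points has a probability of 0.6% to 10.4% for non-healing of 4.5% to 20% (Newcombe), or 0.01% to 0.8% (Wald). A changed primary result is a worst case, and the likely effect is small.

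This is a minor to moderate point, worth acting on because the correction is specific and cheap.

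**What to change.** - **Protocol 5.3(1):** limit removal to non-use for reasons unrelated to the device.
- **SAP 9, FAS:** state that randomised subjects whose assigned screw was opened or attempted stay in the FAS as randomised, are followed to 24 weeks and are scored by the protocol's healing criteria. Add one sensitivity analysis that counts defect-related non-use as not healed.
- **SAP 9, safety set:** keep it exposure-based for adverse events. Count an attempted implantation of either arm's screw as use. Do not add subjects whose package was only opened.
- **Protocol 7.1 and SAP 7C:** report the defects already recorded by arm, as number and percentage of all randomised subjects, stating whether the screw was replaced, abandoned or retained.

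**Cost:** a few lines of text, one table from data already collected, one sensitivity run, and a few extra subjects in follow-up to 24 weeks. The sample size does not change.
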